9.1.1.3 Follow-up (Parts A, B, and C)

Subjects will have a Safety Follow-up Visit 7 to 10 days after the last study drug dose. Safety Follow-up Visit assessments are listed in [Table 3-2](#) (Cohorts A1 through A6), [Table 3-3](#) (Cohort A7), [Table 3-4](#) (Part B), and [Table 3-5](#) (Part C).

9.1.1.4 Early Discontinuation (Parts A, B, and C)

Subjects who prematurely discontinue study drug dosing will be asked to return to the CRU for a Safety Follow-up Visit. Safety Follow-up Visit assessments are listed in [Table 3-2](#) (Cohorts A1 through A6), [Table 3-3](#) (Cohort A7), [Table 3-4](#) (Part B), and [Table 3-5](#) (Part C).

9.1.2 Parts D, E, and F

Part D, which is comprised of Parts D1 and D2, is randomized, double-blind, placebo-controlled and evaluates VX-445 in TC with TEZ/IVA in subjects with CF (F/MF genotypes). Part E is randomized, double-blind, TEZ/IVA-controlled and evaluates VX-445 in TC with TEZ/IVA in subjects with CF (F/F genotype). Part F is randomized, double-blind, placebo-controlled, and evaluates VX-445 in TC with TEZ/VX-561 in subjects with CF (F/MF genotypes). Part F is an optional part of the study, which will be conducted at the sponsor's discretion. All parts are multicenter and designed to evaluate the safety and efficacy of VX-445 in TC.

Approximately 104 subjects with CF will be enrolled. Part D may be initiated while Parts A, B, and C are ongoing after review of safety, tolerability, and PK data. Enrollment of Parts D1 and D2 will be sequential, while enrollment of Parts E and F will be in parallel with Part D2.

After all Part D1 subjects complete the Day 15 Visit, a blinded review of all available safety and PK data will be conducted by the Vertex study team and lead investigator(s). Dosing in Parts D2, E, and F will start after this review, if supported by safety and PK data.

Part E subjects who are participating in Study VX11-661-110 (Study 661-110), an open-label study of TEZ/IVA combination therapy, will not need to washout TEZ/IVA treatment; these subjects will transition directly from their prior treatment to the TEZ/IVA Run-in Period providing that they meet all eligibility criteria. These subjects can have screening assessments for this study done while they are continuing to participate in Study 661-110.

Key study elements are summarized in [Table 9-2](#). The treatment arms and randomization ratios for each part are summarized in [Table 9-3](#). A schematic of the study design is shown in [Figure 9-1](#). Study visits and assessments are shown in [Table 3-6](#) (Parts D1 and D2), [Table 3-7](#) (Part E), and [Table 3-8](#) (Part F).

Table 9-2 Parts D, E, and F: Key Study Elements

Element	Part D1	Part D2	Part E	Part F
Study population				
Genotype(s)	F/MF	F/MF	F/F	F/MF
Age	≥18 years	≥18 years	≥18 years	≥18 years
ppFEV ₁ criteria	≥40 to ≤90	≥40 to ≤90	≥40 to ≤90	≥40 to ≤90
Number of subjects	Approximately 8	Approximately 48	Approximately 24	Approximately 24
Study design	Parallel group	Parallel group	Parallel group	Parallel group
Control	Placebo	Placebo	TEZ/IVA	Placebo

IVA: ivacaftor; MF: minimal function; ppFEV₁: percent predicted forced expiratory volume in 1 second; TEZ: tezacaftor

Table 9-3 Treatment Arms and Planned Doses by Part in the Treatment Period (Period 1)

Part	Treatment Arm	VX-445 Dosage	TEZ Dosage	IVA Dosage	VX-561 Dosage
Part D1^a	TC-mid	100 mg qd	100 mg qd	150 mg q12h	N/A
3:1	Triple placebo	Placebo	Placebo	Placebo	N/A
Part D2^a	TC-high	200 mg qd	100 mg qd	150 mg q12h	N/A
6:4:3:3	TC-mid	100 mg qd	100 mg qd	150 mg q12h	N/A
	TC-low	50 mg qd	100 mg qd	150 mg q12h	N/A
	Triple placebo	Placebo	Placebo	Placebo	N/A
Part E^b	TC-high	200 mg qd	100 mg qd	150 mg q12h	N/A
3:1	TEZ/IVA	Placebo	100 mg qd	150 mg q12h	N/A
Part F	TC2-high	200 mg qd	100 mg qd	N/A	150 mg qd ^c
3:1	Triple placebo	Placebo	Placebo	N/A	Placebo

TC2: triple combination 2 (VX-445/TEZ/VX-561); IVA: ivacaftor; N/A: not applicable; q12h: every 12 hour; qd: once daily; TC: triple combination (VX-445/TEZ/IVA); TEZ: tezacaftor

^a In Parts D1 and D2, all subjects will also receive TEZ 100 mg qd/IVA 150 mg q12h or dual placebo during Period 2.

^b In Part E, all subjects will also receive TEZ 100 mg qd/IVA 150 mg q12h during the Run-in Period and the Washout Period, which is the dosage evaluated in Phase 3 studies of TEZ/IVA.

^c See [Section 9.3.2.2](#) for information relating to the selection of the VX-561 dose.

Figure 9-1 Parts D, E, and F: Schematic of Study Design

Part D1: F/MF

N ~ 8

Randomization: 3:1

	Period 1 (4 weeks)		Period 2 (1 week)	
Screening Period (4 weeks)	TC-mid (VX-445/TEZ/IVA)	N = 6	TEZ/IVA	Safety Follow-up Period (4 weeks)
	Triple Placebo	N = 2	Dual Placebo	

Part D2: F/MF

N ~ 48

Randomization: 6:4:3:3

Stratification: ppFEV₁: ≥70 versus <70

	Period 1 (4 weeks)		Period 2 (1 week)	
Screening Period (4 weeks)	TC-high (VX-445/TEZ/IVA)	N = 18	TEZ/IVA	Safety Follow-up Period (4 weeks)
	TC-mid (VX-445/TEZ/IVA)	N = 12		
	TC-low (VX-445/TEZ/IVA)	N = 9		
	Triple Placebo	N = 9	Dual Placebo	

Part E: F/F

N ~ 24

Randomization: 3:1

Stratification: ppFEV₁: ≥70 versus <70

	Run-in Period (4 weeks)	Period 1 (4 weeks)	Washout Period (4 weeks)	
Screening Period (4 weeks)	TEZ/IVA	TC-high (VX-445/TEZ/IVA)	TEZ/IVA	Safety Follow-up Period (4 weeks)
		Placebo + TEZ/IVA		

Part F (if Conducted): F/MF

N ~ 24

Randomization: 3:1

Stratification: ppFEV₁: ≥70 versus <70

		Period 1 (4 weeks)			
Screening Period (4 weeks)	TC2-high (VX-445/TEZ/VX-561)		N = 18	Safety Follow-up Period (4 weeks)	
	Triple Placebo		N = 6		

TC2: triple combination 2 (VX-445/TEZ/VX-561); IVA: ivacaftor; MF: minimal function; N: number of subjects; ppFEV₁: percent predicted forced expiratory volume in 1 second; TC: triple combination (VX-445/TEZ/IVA); TEZ: tezacaftor

Note: to maintain the blind, matching placebo tablets will be administered, as applicable, so that all subjects receive the same number of tablets within a given dosing period.

9.1.2.1 Screening (Parts D, E, and F)

Screening will occur within 28 days before the first dose of study drug. Screening assessments will be used to confirm that subjects meet the eligibility criteria for the study. See [Table 3-6](#), [Table 3-7](#), and [Table 3-8](#).

9.1.2.1.1 Repetition of Screening Assessment(s) (Parts D, E, and F)

If screening spirometry measurements fail to meet acceptability and repeatability criteria as specified by American Thoracic Society/European Respiratory Society guidelines¹⁴, repeat spirometry evaluation may be performed.

Otherwise, repeating individual screening assessment(s) that did not meet eligibility criteria is not permitted, with the following exceptions that require the approval of the medical monitor:

- If there is clear evidence of a damaged sample, laboratory error, or equipment malfunction, collection of a repeat sample for the appropriate laboratory test or assessment may be permitted.
- Exclusionary liver function test results, which may be retested once within 14 days of the original screening date.
- Assessments required for eligibility may be repeated if permitted, as described in [Section 8.2](#).
- If the screening G6PD value is exclusionary, it may be repeated by the site following the conduct described in [Section 11.7.2](#).

If repeat values of the individual assessment(s) are within the eligibility criteria and completed within the screening window, then the subject is eligible for the study.

9.1.2.1.2 Rescreening (Parts D, E, and F)

Subjects may only be rescreened with the approval of the medical monitor. If a subject is rescreened, all screening assessments will be repeated except for *CFTR* genotyping, FSH level (if serum FSH level was ≥ 40 mIU/mL during prior screening), G6PD activity test, and the sweat chloride concentration. If a subject is rescreened, the new screening window will begin once the first rescreening assessment has been initiated.

9.1.2.1.3 Extension of Screening Period Window (Parts D, E, and F)

A subject may have the Screening Period window extended without medical monitor approval by 2 weeks for the following reasons:

- Repetition of the Screening Period assessments ([Section 9.1.2.1.1](#))
- Unexpected operational or logistic delays, or to meet the eligibility criteria
- Repetition of spirometry assessment if results are of poor quality

A subject may have the Screening Period window extended for an additional 2 weeks (total of 4 weeks) with medical monitor approval.

9.1.2.2 Stratification and Randomization (Parts D, E, and F)

All subjects will have a spirometry assessment done at the Screening Visit. Subjects in Part E may have an additional spirometry assessment done for stratification purposes before randomization based on prior *CFTR* modulator treatment.

9.1.2.2.1 Stratification (Parts D, E, and F)

Part D1

No ppFEV₁ stratification will be performed.

Part D2

ppFEV₁ stratification (<70 versus ≥ 70) will be performed using the screening (Days -28 to -1) ppFEV₁ value.

Part E

ppFEV₁ stratification (<70 versus ≥ 70) will be performed using a value obtained at the following visit:

- Screening Visit (Days -56 to -29) for subjects transitioning directly from at least 14 days of uninterrupted TEZ/IVA treatment
- Day -14 Visit (+ 13 days) for all other subjects

Part F

ppFEV₁ stratification (<70 versus ≥ 70) will be performed using the screening (Days -28 to -1) ppFEV₁ value.

9.1.2.2 Randomization (Parts D, E, and F)

Randomization will occur before the first dose of study drug and may be done on either Day -1 or Day 1, after all inclusion and exclusion criteria have been satisfied and the criteria for entry into the Treatment Period have been confirmed (see [Section 9.1.2.4](#)).

9.1.2.3 Run-in Period (Part E)

The Run-in Period of Part E is 4 weeks and is designed to establish a reliable on-treatment (TEZ/IVA) baseline for the Treatment Period (Period 1). Subjects will receive TEZ 100 mg qd/IVA 150 mg q12h during the Run-in Period. The first dose of TEZ/IVA will be administered at the Day -28 Visit. The last dose of TEZ/IVA within the Run-in Period will be administered on Day -1 (1 day before the Day 1 Visit).

Study eligibility for Part E subjects will be confirmed before the first dose of TEZ/IVA in the Run-in Period (on the Day -28 Visit). Subjects who prematurely discontinue TEZ/IVA during the Run-in Period will not be randomized or participate in the Treatment Period (Period 1), unless they rescreen and complete a 4-week Run-in Period ([Section 9.1.2.1.2](#)).

Study visits during the Run-in Period will occur as shown in [Table 3-7](#).

9.1.2.4 Treatment Period (Parts D, E, and F)

To be eligible to continue into the Treatment Period, subjects must have stable CF disease and have remained on stable CF medication regimen during the 28 days before the Day 1 Visit AND must not have had an acute non-CF illness within 14 days before the Day 1 Visit.

The VX-445 treatment duration is 4 weeks. The Treatment Period duration is approximately 5 weeks for Parts D1 and D2 (Period 1 + Period 2), 4 weeks for Part E (Period 1), and 4 weeks for Part F (Period 1). All study periods will be conducted as described in [Section 9.1](#). Study drug administration details are provided in [Section 9.6.2](#).

9.1.2.5 Washout Period (Part E)

The Washout Period of Part E will last approximately 4 weeks and is designed to evaluate the effect on PD and efficacy endpoints as subjects step down from TC to TEZ/IVA. Subjects will receive TEZ 100 mg qd/ IVA 150 mg q12h during the Washout Period.

9.1.2.6 Follow-up (Parts D, E, and F)

There will be a Safety Follow-up Visit occurring approximately 28 days after the last dose of study drug for subjects who complete study drug dosing and for subjects who prematurely discontinue study drug dosing.

A subject who was enrolled in Study 661-110 and then enrolled in Part E of this study can re-enroll in Study 661-110 after completing the Washout Period of this study. If the subject completes the Day 57 Visit of this study and then re-enters Study 661-110, the subject will not have a Safety Follow-up Visit in this study.

9.1.2.7 Early Termination of Treatment (Parts D, E, and F)

If a subject prematurely discontinues treatment, an Early Termination of Treatment (ETT) Visit should be scheduled as soon as possible after the decision to terminate study drug treatment. All subjects who prematurely discontinue treatment (other than those who re-enroll in

Study 661-110, as described in [Section 9.1.2.6](#)) will also be required to complete the Safety Follow-up Visit, approximately 28 days after their last dose of study drug.

If the ETT Visit occurs 3 weeks or later following the last dose of study drug, the ETT Visit will replace the Safety Follow-up Visit, and a separate Safety Follow-up Visit will not be required.

If a subject withdraws from the study and also withdraws consent for disclosure of future information, no further evaluations should be performed and no additional data should be collected. Vertex may retain and continue to use any data and samples collected before such withdrawal of consent.

9.1.2.8 Independent Data Monitoring Committee (Parts D, E, and F)

This study will be monitored by an independent data monitoring committee (IDMC), which will conduct reviews of safety data from all parts of the study. The IDMC Charter, which will be finalized before the first subject is screened, will include procedural details of the IDMC structure and function, triggers for meetings, and plans for data to be reviewed. The IDMC Chair will review available safety and PK data from Parts A, B, and C of the study prior to commencement of dosing in Part D1 to determine if it is appropriate to proceed with the study.

9.2 Method of Assigning Subjects to Treatment Groups

A randomization list for each part will be produced by Vertex Biostatistics or a qualified randomization vendor. The Vertex study biostatistician will review and approve the dummy randomization list. The final randomization list will be reviewed and approved by a designated unblinded biostatistician who is not a member of the study execution team (SET).

Only subjects who have completed screening assessments and are eligible for participation in the study will be randomized to receive active study drug or placebo. Randomized subjects will be assigned a unique subject number.

For Parts A, B, and C, a list identifying subjects by their subject number will be maintained in the study file at the CRU.

For Parts D, E, and F, an interactive web response system (IWRS) will be used to assign subjects to treatment.

9.3 Rationale for Study Design and Study Drug Regimens

9.3.1 Study Design

9.3.1.1 Parts A, B, and C

Parts A (except Cohort A7) and B have a parallel-group, dose-escalation design, with each subject participating in only 1 cohort to avoid PK and/or PD carryover effects.

VX-445 is being developed in TC with TEZ/IVA for the treatment of CF, and subjects with CF will be dosed with the TC in Parts D and E of this study (see [Section 9.3.1.2](#)). Part C of this study is included to evaluate the safety, tolerability, and PK of the TC in healthy subjects before subjects with CF are dosed with the TC.

Parts A (except Cohort A7), B, and C will be randomized, double-blind, and placebo-controlled in order to avoid bias in the collection and evaluation of safety and tolerability data during study conduct. Placebo was chosen as the control treatment to assess whether any observed effects are treatment-related or simply related to the study conditions.

Staggered Dosing in Cohorts A1 and C1

In Cohorts A1 and C1, after the first 2 subjects are dosed (1 active, 1 placebo), there will be at least a 24-hour observation period before the remaining subjects in Cohorts A1 and C1 are dosed. Staggered dosing will be used in Cohort A1 because this is the first time VX-445 will be administered to humans. In addition, staggered dosing is proposed for Part C as it is the first time VX-445 will be administered in TC with TEZ/IVA in humans. Staggered dosing for Part B is not considered necessary because the total daily dose in the first cohort (Cohort B1) will be at least 1 dose level below the highest Part A dose for which safety, tolerability and PK results are available and that is safe and well tolerated. Therefore, the relative risk to subjects dosed in Cohort B1 is considered to be less than that of subjects in Cohorts A1 and C1.

Cohort A7

Cohort A7 will not be initiated until all data required to support administration of the VX-445 tablet and IV formulations are available. Subjects in Cohort A7 will receive up to 3 single doses of VX-445: 2 single oral doses of tablet (dose to be determined [TBD] pending PK data from previous Part A cohorts, but not to exceed the highest dose that was safe and well tolerated) and a single IV dose (the planned dose is 20 mg, but may be adjusted pending data from previous Part A cohorts; however, the final selected dose will not be predicted to exceed the highest exposure that was safe and well tolerated). Each dosing occasion will be separated by at least 6 days. Based on nonclinical data, the interval between dosing occasions is considered adequate to minimize any potential for carryover. However, the washout interval of 6 days may be increased if needed based on emerging PK data from earlier Part A cohorts.

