Cohort A7 has an open-label, single sequence design in which subjects will receive a single dose of VX-445 on up to 3 dosing occasions with at least 6-day washouts between dosing occasions. VX-445 doses include 2 single oral doses of tablet (dose to be determined [TBD], pending PK data from previous Part A cohorts, but will not exceed the highest dose that was safe and well tolerated) and a single IV dose (the planned dose is 20 mg, which may be adjusted pending data from previous Part A cohorts, but will not be predicted to exceed the highest exposure that was safe and well tolerated). If the IV formulation or the data supporting the use of the IV formulation are not available, then the third dosing period, in which subjects receive the IV dose, will not be conducted.

Part B may be initiated while Part A is ongoing after review of safety, tolerability, and PK data. The total daily dose in the starting cohort (Cohort B1) will be at least 1 dose level below the highest Part A dose for which safety, tolerability, and PK results are available and that is safe and well tolerated.

Part C may be initiated while Parts A and B are ongoing after review of safety, tolerability, and PK data. The VX-445 starting dose (Cohort C1) will be at least 1 dose level below the highest Part B dose for which safety and tolerability results are available and supportive. The dosage of TEZ/IVA in the TC will be TEZ 100 mg once per day (qd)/IVA 150 mg every 12 hours (q12h).

Dosing will be staggered in Cohort C1, with 2 subjects dosed (1 with VX-445 in TC with TEZ/IVA and 1 with triple placebo) at least 24 hours before the remaining 6 subjects. Staggering at higher doses may be conducted if deemed necessary based on review of emerging safety data.

Parts D, E, and F (Subjects With CF)

Part D, which is comprised of Parts D1 and D2, is randomized, double-blind, placebo-controlled, and evaluates VX-445 in TC with TEZ/IVA in subjects with CF (F/MF genotypes).

Part E is randomized, double-blind, TEZ/IVA-controlled, and evaluates VX-445 in TC with TEZ/IVA in subjects with CF (F/F genotype).

Part F, an optional part of the study which will be conducted at the sponsor's discretion, is randomized, double-blind, placebo-controlled, and evaluates VX-445 in TC with TEZ and VX-561 in subjects with CF (F/MF genotypes).

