AE: adverse event; CRU: clinical research unit; ECG: electrocardiogram; ICF: informed consent form; IV: intravenous; PE: physical examination; PK: pharmacokinetic

^h Blood samples for PK assessments will be collected on Days 1 and 7 before dosing (0 hours) and at 0.5, 1, 1.5, 2, 3, 4, 5, 6, 8, 12, 24 (Days 2, 8), 36 (Days 2, 8), 48 (Days 3, 9), 72 (Days 4, 10), 96 (Days 5 and 11), and 120 (Days 6 and 12) hours postdose. Blood samples for PK assessments will be collected on Day 13 before dosing (0 hours, before the start of the IV infusion) and at 0.5 (after the end of the IV infusion), 0.75, 1, 1.25, 1.5, 2, 3, 4, 5, 6, 8, 12, 24 (Day 14), 36 (Day 14), 48 (Day 15), 72 (Day 16), and 96 hours (Day 17) after the start of the IV infusion. Acceptable PK sampling windows are provided in [Table 11-1](#).

ⁱ If Dosing Period 3 is not conducted, a blood sample for PK assessment will be collected on Day 13 (144 hours after dosing on Day 7).

^j Study drug will be administered as a tablet in the fasted state on Day 1 and in the fed state on Day 7. On Day 13, study drug will be administered in the fed state as a single IV dose infused over 30 minutes (See [Section 9.6.1.1](#) for details). If the IV dose is not administered, subjects will be discharged on Day 13 after completion of the study visit assessments.

^k If data to support use of the IV dose is not available, Dosing Period 3 will not be conducted and subjects will not receive the IV dose.

^l All medications taken from 28 days before the first dose of study drug through the end of the study will be recorded.

Table 3-4 Study VX16-445-001: Part B, Treatment Period and Safety Follow-up Visit

Event/Assessment ^a	Study Day															Safety Follow-up Visit (7 to 10 Days After Last Dose of Study Drug)
	-1	1	2	3	4	5	6	7	8	9	10	11	12	13	14	
Inpatient days	X	X	X	X	X	X	X	X	X	X	X	X	X	X	X ^b	
Outpatient visits																X
Randomization		X														
Weight ^c	X										X					
Standard 12-lead ECG ^d	X	X				X										X
Vital signs ^e	X	X	X	X	X	X	X	X	X	X	X	X	X	X	X	X
Full PE	X															X
Serum chemistry	X		X		X		X				X					X
Hematology	X		X		X		X				X					X
4β-hydroxycholesterol		X									X					
Blood for PK analysis ^f		X	X	X	X						X	X	X	X	X	
Drug test (urine or blood), including cotinine	X															
Alcohol test (urine, blood, or breath)	X															
Urinalysis																X
Spirometry ^g	X	X								X						

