^a The Washout Period is a minimum of 6 days and may be increased as needed based on emerging data from earlier cohorts (Cohorts A1 through A6). Subjects in Cohort A7 will receive a single dose of VX-445 on up to 3 dosing occasions. VX-445 doses include 2 single oral doses of tablet (dose TBD, pending PK data from previous Part A cohorts, but will not exceed the highest dose that was safe and well tolerated) and a single IV dose (the planned dose is 20 mg, but may be adjusted pending data from previous Part A cohorts; however, the final selected dose will not be predicted to exceed the highest exposure that was safe and well tolerated). If the IV formulation or the data supporting the use of the IV formulation are not available, then the third dosing period, in which subjects receive the IV dose, will not be conducted. If the IV dose is not administered, subjects will be discharged from the CRU on Day 13 after completing all study visit assessments and will return for a Safety Follow-up Visit ([Table 3-3](#)).

^b The dosage of TEZ/IVA will be TEZ 100 mg qd/IVA 150 mg q12h which will be administered as TEZ 100-mg/IVA 150-mg FDC in the morning and IVA 150 mg in the evening.

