Unless otherwise specified, the analyses will be done by Treatment Group in all cohorts for Parts A, B and C. Separate summary tables will be produced for each part.

- Part A (Cohorts A1 through A5): Placebo, VX-445 20 mg, VX-445 60 mg, VX-445 120 mg, VX-445 240 mg, VX-445 360 mg, and VX-445 Total. The dose levels are subject to change to reflect the real dose levels.

- Part A (Cohort A7): tablet [fasted] 100 mg, tablet [fed] 100 mg and IV [fed] 20 mg.

- Part B: Placebo, VX-445 60 mg QD, VX-445 120 mg QD, VX-445 240 mg QD, VX-445 340 mg QD and VX-445 Total.

- Part C: Triple Placebo, VX-445 200 mg QD + TEZ/IVA, VX-445 280 mg QD + TEZ/IVA, VX-445 100 mg QD + TEZ/IVA and VX-445 + TEZ/IVA Total.

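### Cohort A7 gives the fasted tablet before the fed tablet in every subject, so food effect is confounded with period; carryover into the fed and IV profiles is possible but conditional

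*Protocol*

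**What the plan says.** Protocol Section 6.2 lists food effect and absolute bioavailability among the secondary objectives of Part A. Only Cohort A7, with 8 subjects (Table 9-1), can address them.

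- **Order.** The Synopsis states: "Cohort A7 has an open-label, single sequence design". Table 3-3, footnote j, fixes the tablet periods: "Study drug will be administered as a tablet in the fasted state on Day 1 and in the fed state on Day 7". The IV period follows: "On Day 13, study drug will be administered in the fed state as a single IV dose infused over 30 minutes".
- **Doses.** Section 9.1 of the SAP for Parts A, B and C gives: "Part A (Cohort A7): tablet [fasted] 100 mg, tablet [fed] 100 mg and IV [fed] 20 mg".
- **Interval.** Table 9-1, footnote a: "The Washout Period is a minimum of 6 days and may be increased as needed based on emerging data from earlier cohorts". Section 9.3.1.1 calls the interval adequate on nonclinical grounds ("Based on nonclinical data, the interval between dosing occasions is considered adequate to minimize any potential for carryover") and then adds: "However, the washout interval of 6 days may be increased if needed based on emerging PK data from earlier Part A cohorts". Table 3-3 and the treatment-emergent periods in SAP Section 9.1 are laid out on Days 1, 7 and 13, so 144 h apart.
- **Samples and methods.** Table 3-3, footnote h, schedules predose PK samples on Days 1, 7 and 13. Protocol Section 12.4.1.1 names noncompartmental analysis with descriptive statistics and leaves the detail to the clinical pharmacology analysis plan (CPAP), which is not among the documents.

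**The concern.** With one order for all subjects, the fed-minus-fasted difference is also the Day 7-minus-Day 1 difference. Any change over time is counted as a food effect. Drug left from Day 1 can only raise the fed AUC. Protocol Section 9.3.2.1 predicts only a mild food effect, so a shift of a few percent is not trivial beside the quantity being estimated.

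The IV period raises a second question. A 20 mg dose follows two 100 mg tablets, so residue that is small against a tablet profile is larger, relatively, against the IV profile. If it were present and not removed, it would enlarge the denominator of absolute bioavailability and lower the estimate. A larger cohort would remove neither bias.

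**Working it through.** The plan states no half-life, F, carryover fraction or power for A7, so there is no figure to reproduce. The confounding needs no arithmetic. The carryover does, and is shown over a range.

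**Inputs from the documents.** Oral 100 mg and IV 20 mg, ratio 100/20 = 5 (SAP 9.1). Interval 144 h at the planned minimum (Table 3-3).

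**Assumptions.** Linear one-compartment PK, true food effect ratio of 1, AUC to infinity without correction, half-life 12 to 48 h, F 0.5 to 1.0.

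**Formulas.** Let r = 2^(−144/half-life), the fraction of a tablet AUC still to come when the next dose is given.

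- Fed/fasted AUC ratio is multiplied by 1 + r.
- IV AUC is multiplied by 1 + 5F(r + r²); r is the Day 7 residue and r² the Day 1 residue.
- Apparent F, fed tablet as reference, is F(1 + r)/[1 + 5F(r + r²)].
- With the fasted tablet as reference it is F/[1 + 5F(r + r²)].

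**Numbers for F = 0.8.**

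- 18 h: r = 2^(−8) = 0.0039. IV: 4 × (0.0039 + 0.00002) = 1.6%. Apparent F = 0.79.
- 24 h: r = 2^(−6) = 0.0156. IV: 4 × (0.0156 + 0.0002) = 6.3%. Apparent F = 0.8 × 1.0156/1.0635 = 0.764.
- 36 h: r = 2^(−4) = 0.0625. IV: 4 × (0.0625 + 0.0039) = 26.6%. Apparent F = 0.8 × 1.0625/1.2656 = 0.672.

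Adding first-order absorption (assumed rate 1/h) changes these only slightly:

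| Half-life | Fed/fasted ratio | IV AUC, F = 0.8 (F = 0.5 to 1.0) | Bias in F, fed reference, F = 0.8 | Bias in F, fasted reference, F = 0.8 |
|---|---|---|---|---|
| 12 h | 0.0% | +0.1% (0.06 to 0.13) | −0.1% | −0.1% |
| 18 h | +0.4% | +1.6% (1.0 to 2.0) | −1.2% | −1.6% |
| 24 h | +1.6% | +6.5% (4.1 to 8.2) | −4.6% | −6.1% |
| 36 h | +6.4% | +27.1% (16.9 to 33.9) | −16.3% | −21.3% |
| 48 h | +12.7% | +57.1% (35.7 to 71.3) | −28.3% | −36.3% |

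**Direction.** With the fed reference, apparent F is below true F when 1 + r < 1 + 5F(r + r²), that is, when F > 0.2/(1 + r). So the bias is downward for any F above about 0.2.

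**Effect of a balanced tablet order.** With a true food ratio of 1, the fasted-first order shows a fed/fasted ratio of 1 + r and the fed-first order shows 1/(1 + r). Their geometric mean is √[(1 + r)/(1 + r)] = 1. Carryover common to both orders cancels, as does any other common period effect.

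**Effect of a longer interval alone, for illustration only.** At 288 h and F = 0.8, IV inflation is 0.1%, 1.6% and 6.4% for half-lives of 24, 36 and 48 h. The confounding of food with period is unchanged.

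**The case against.** Much can be said for the plan.

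- **The interval is not fixed.** It is a minimum, and human PK from the earlier Part A cohorts is the stated ground for lengthening it. This stands, although no threshold is given and the schedule and SAP show Days 1, 7 and 13.
- **The half-life may be short.** This also stands. At 18 h or less there is almost nothing to correct. If distribution phases contribute to AUC, the one-compartment model also overstates the residue for a given terminal half-life.
- **The correction may exist where it cannot be seen.** PK methods belong in the CPAP, and the SAP for Parts A, B and C covers safety only. The text after the IV dose rationale in Protocol 9.3.2.1 is blacked out, so one cannot say that the smaller IV dose was overlooked. Predose samples on Days 7 and 13 make residue measurable. This stands for carryover. It does not help with period, because no analysis can separate food from period within one sequence.
- **IV last has a reason.** The IV period is dropped if its formulation or supporting data are unavailable. This stands, and the fix keeps it last.
- **The bias is small beside the imprecision.** With 8 paired subjects and an assumed within-subject CV of 15% to 25%, the 90% interval half-width on the log scale is about 1.895 × √2 × CV/√8, or 0.14 to 0.24. The upper limit is then about 15% to 27% above the estimate. The objectives are descriptive, the other healthy-subject cohorts and all CF parts are dosed fed, and no dosing decision shown depends on the fed/fasted ratio. This lowers the severity but does not remove the confounding.
- **A7 may already have been dosed.** Protocol 9.3.2.2 reports Part A tolerability results and the SAP lists the A7 doses. If so, only analysis and reporting can change.

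**Conclusion.** The design point holds: in Cohort A7 the food effect is fully confounded with period and with any Day 1 carryover. That follows from the written order and rests on no assumption about the drug.

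The carryover point is conditional. It needs three things together: the interval left at 144 h, a terminal half-life of about 24 h or more, and uncorrected profiles. The fed/fasted AUC ratio would then rise by about 1.6% at 24 h and 6% at 36 h. With F = 0.8 the IV AUC would rise by about 6% and 27%, and absolute bioavailability would be biased downward. Half-life and F are assumptions, since the documents give neither.

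A reader might infer that 6 days is a fixed interval, that residual drug does inflate the IV AUC, and that the predose samples go unused. The documents do not support this: the interval may be lengthened, no human half-life is stated, and the plan that would hold the correction rule is not available here.

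Severity is minor, because both objectives are secondary and descriptive and no hypothesis test depends on them.

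**What to change.** **Main change.** Randomise the order of the two tablet periods over Days 1 and 7: 4 subjects fasted then fed, 4 fed then fasted. Keep the IV period last so that it can still be dropped. Estimate the food effect on log AUC and log Cmax with period and sequence terms. The cost is a small randomisation list for an open-label cohort and one or two degrees of freedom. No dose, visit or sample is added. This does not address carryover into the IV period.

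**Secondary.** Confirm in the CPAP that:

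- the Day 7 and Day 13 profiles are corrected for residual drug from the scheduled predose samples, for example by subtracting the predose concentration decayed at the subject's own terminal rate, with corrected and uncorrected results both reported;
- the interval used is supported by human PK from Cohorts A1 to A6, not by nonclinical data alone.

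This costs a few lines of text.

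**If A7 has already been dosed,** apply the correction and state in the report that the food effect cannot be separated from period.
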